#### 3.5.2. Blinding/Masking and Planned Unblinding

An unblinded pharmacist will prepare each vaccine, and an unblinded qualified medical professional will administer the vaccine in such a way that the participant cannot see the syringe. Unblinded staff may also schedule study visits and conduct procedures other than clinical endpoint assessments. Staff performing clinical assessments will not know whether a participant is receiving placebo or vaccine, or which vaccine a participant is receiving at the first visit. During a follow-up call, scheduled 3 days after the first vaccination/placebo dose, participants will be scheduled for their next dose.

Under protocol versions 1.0 - 4.0, participants and the staff were unblinded during the follow-up call 3 days after the second injection when a third appointment (for those who received a placebo injection first) was, or was not (active vaccinations only) scheduled. Due to the different dosing schedules for the Pfizer-BioNTech COVID-19 Vaccine and Moderna COVID-19 Vaccine, it became apparent to both the site staff and study participant which vaccine had been assigned, once their second injection was scheduled.

Under protocol versions 5.0 – 8.0, the participant, their parents/legal guardians, and staff will be aware of whether a participant received placebo at the phone call 3 days after the first injection when the participant is scheduled for the first active vaccine in approximately 7 days after placebo. Participants, their parents/legal guardians, and staff will not be blinded to vaccine assignment as only one active vaccine will be implemented at a given time.

Vaccination reports to the state and local authorities will be completed after a participant is unblinded.

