### **9.5. Participants Randomized to Receive Placebo Under Protocol Versions 5.0 – 8.0**

#### **9.5.1. First Vaccination Visit (Day 8; + 14 Days)**

Participants randomized to placebo will be asked to return to clinic to receive their first vaccine injection, approximately 7 days, after they received the placebo. In addition to receiving the Pfizer-BioNTech COVID-19 Vaccine or Moderna COVID-19 Vaccine, the participant will complete the same study procedures as those conducted during the Enrollment Visit, with the exception of growth parameters and pre-vaccination blood sample collections. ([Section 9.2 Enrollment Visit \[Day 1\]](#)). Following vaccination, the study participant will be observed for 90 minutes for AEs, including examination of the injection site, and have vital sign measurements. Participants will have blood collected 30-60 minutes after the onset of an allergic reaction. Sample collections post vaccination will be based on participant weight, detailed further in the MOP.

In addition, the study team will complete a review of the participant's diary and distribute an additional diary, as needed.

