7.2.2. Primary Analysis of the Primary Endpoint

If systemic allergic reactions are observed, we will compare the proportions of participants experiencing a systemic allergic reaction to the Pfizer-BioNTech COVID-19 Vaccine and independently to the Moderna COVID-19 Vaccine between the HA/MCD and comparison populations. The point estimate of the difference in proportions between populations within each vaccine is estimated as p_1-p_0 with $p_1=x_1/n_1$ and $p_0=x_0/n_0$ and will be reported, together with the corresponding 95% exact unconditional confidence interval. The proportion difference will be tested using a Barnard's Exact Unconditional Test with a two-sided test using the central method of doubling the one-sided p-value. No multiplicity adjustment will be applied to these two primary endpoints.

```
*** Primary Analysis (Barnard's);
ods output BarnardsTest=BarnardsTestOutput;
proc freq data = d_1 order = data;
  title "Primary";
  where dose = 'E' and protocol<5;
  tables group*resp / riskdiff;
  exact riskdiff barnard;
* High computational power, only run on an as needed basis;
run;
```

The p-value is equal to (BARNARDSTESTOUTPUT.NVALUE1)*2 where BARNARDSTESTOUTPUT.NAME1='XPL_RDIF1'.

```

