7.3. Secondary Endpoints

All secondary endpoints will be analyzed for participants enrolled under version 1.0 through 4.0. If sufficient numbers of children are enrolled, then adults 18 years of age and older will be also be analyzed separately from children.

7.3.1. Secondary Endpoint 1

Endpoint: The proportion of participants who experience a severe (Grade 3 or higher per [CoFAR Grading Scale for Systemic Allergic Reactions Version 3.0](#)) systemic allergic reactions within the 90-minute post-vaccination observation period to either dose of each vaccine.

Computation: A Grade 3 or higher systemic allergic reaction, categorized as yes or no, is defined as a participant having a Grade 3 or higher (per CoFAR Grading Scale V3.0) systemic allergic reaction to either active dose 1 or active dose 2 (categorized as yes) or to neither active dose (categorized as no).

Participants who do not have a systemic allergic reaction to the 1st active dose but missing data for their 2nd active dose will be removed from this analysis (complete case analysis).

Analysis: This analysis will be carried out as outlined in Section 7.2.2. A sensitivity analysis will be carried out as outlined in Section 7.2.3.

7.3.2. Secondary Endpoint 2

Endpoint: The proportion of participants who experience an anaphylactic reaction (Levels 1-3) per Brighton Collaboration Criteria within the 90-minute post-vaccination observation period to either dose of each vaccine.

Computation: An anaphylactic reaction (Levels 1-3) per Brighton Collaboration Criteria, categorized as yes or no, is defined as a participant having an anaphylactic reaction (Levels 1-3) per Brighton Collaboration Criteria to either active dose 1 or active dose 2 (categorized as yes) or to neither active dose (categorized as no).

Participants who do not have a systemic allergic reaction to the 1st active dose but missing data for their 2nd active dose will be removed from this analysis (complete case analysis).

Analysis: This analysis will be carried out as outlined in Section 7.2.2. A sensitivity analysis will be carried out as outlined in Section 7.2.3.

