7.3.3. Secondary Endpoints 3/4

Objective (paired)
Assess the proportion of participants with systemic allergic reactions to the Pfizer-BioNTech COVID-19 Vaccine in the HA/MCD population by dose
Endpoint
The proportion of participants who experience a systemic allergic reaction (CoFAR Grade 2 and above regardless of tryptase, or CoFAR Grade 1 with elevated tryptase [1.2 x baseline plus 2 ng/ml]) within the 90-minute post-vaccination observation period to the first dose and to the second dose conditional on no systemic allergic reaction to the first dose.
Statistical Test
Endpoint will be analyzed using an exact McNemar's test.
Checks & Diagnostics
This analysis will not be carried out if there are no systemic allergic reactions.
Model Results Presentation
Proportions and 95% exact confidence intervals will be presented for the 1 st and 2 nd dose. The mid p-value will be reported using an exact McNemar's test.
Placebo & Pfizer -BioNTech COVID-19 Vaccine (1 st)

Placebo & Pfizer -BioNTech COVID-19 Vaccine (2nd)

Placebo + Pfizer	placebo	1 st	2 nd
Pfizer	1 st	2 nd	

SAS Code

```
*** Paired doses;
proc freq data = d_w order=data;
  title "Paired";
  where group = 'HA/MCD';
  tables D1*D2 / riskdiff;
  exact mcnem riskdiff / midp;
run;
```

R Code

```
library(exact2x2)
t <- with(d_w %>% filter(group == 'HA/MCD'), table(D1, D2))
mcnemar.exact(t, conf.level=.95)
mcnemarExactDP(n=sum(t),
  m=t[1,2]+t[2,1],
  x=t[2,1])
```

Supportive Statistical Analyses

A sensitivity analysis will be performed using a GEE logistic regression model & NLMeans macro to obtain the proportion difference and 95% confidence interval. There will be no adjustment for covariates.

```
*** Paired doses (Sensitivity);
proc genmod data = d_l;
  title "Paired (Sensitivity)";
  where dose in ('D1','D2') & group = 'HA/MCD';
  class id dose;
  model resp(event = '1') = dose / dist=binomial link = logit;
  repeated subject=id / type = ind;
  lsmeans dose / e ilink diff exp;
  store out=genmod;
  ods output coef = coeffs;
run;
%NLMeans(instore=genmod, coef=coeffs, link=logit, title= Paired Prop
Diff);
```

Handling of Missing Data

Participants with missing data for their 2nd active dose for reasons other than systemic allergic reactions in their 1st active dose will be removed from this analysis (complete case analysis).

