Participants with missing data for their 2nd active dose because of a systemic allergic reaction to their 1st active dose (inherent missingness given the current design) will be examined using an extreme case scenario (replacement of all 2nd active dose missing by either yes or no). If the results from this extreme case scenario differs and if there is at least 10 systemic allergic reactions in the 1st active dose a tipping point analysis will be conducted.

Notes

The same analysis will be repeated for the Moderna COVID-19 Vaccine.

Objective (priming)

Assess the difference in proportions of participants with systemic allergic reactions after the second Pfizer-BioNTech COVID-19 Vaccine dose (not placebo arm) versus the first vaccine dose within the placebo arm in the HA/MCD population.

Endpoint

The proportion of participants who experience a systemic allergic reaction (CoFAR Grade 2 and above regardless of tryptase, or CoFAR Grade 1 with elevated tryptase [1.2 x baseline plus 2 ng/ml]) within the 90-minute post-vaccination observation period to the second dose conditional on no systemic allergic reaction to the first dose in the Pfizer-BioNTech COVID-19 Vaccine arm and the first active dose in the Placebo- Pfizer-BioNTech COVID-19 Vaccine arm.

Model Specification

- Endpoint is as defined above.
- Endpoint will be analyzed using Barnard's unconditional exact test.

Model Checking & Diagnostics

This analysis will not be carried out if there are no systemic allergic reactions in the 1st dose among the placebo arm and/or 2nd dose among the Pfizer arm.

Model Results Presentation

Proportions, 95% exact unconditional confidence intervals and p-value will be presented for the 1st dose among Placebo & Pfizer and 2nd dose among the Pfizer arm.

Placebo & Pfizer-BioNTech COVID-19 Vaccine (1st)

Pfizer-BioNTech COVID-19 Vaccine (2nd)

Placebo + Pfizer	placebo	1 st	2 nd
Pfizer	1 st	2 nd	

SAS Code

```
*** Priming;
proc freq data = d_1;
  title "Priming";
  where group = 'HA/MCD' &
    ((dose = 'D1' & Placebo = 'Yes') | (dose = 'D2' & Placebo = 'No'));
  tables dose*resp / riskdiff;
```

```
exact riskdiff barnard;
run;
```

Supportive Statistical Analyses

If there is an issue with the calculation of the Barnard's Exact Unconditional Test, we will perform a univariate logistic regression.

```
*** Priming (Sensitivity);
proc genmod data = d_1;
  title "Priming (Sensitivity)";
  where group = 'HA/MCD' &

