    ((dose = 'P1' & Placebo = 'Yes') |
    (dose = 'D1' & Placebo = 'No' ));
  tables dose*resp / riskdiff;
  exact riskdiff barnard;
run;
```

Supportive Statistical Analyses

If there is an issue with the calculation of the Barnard's Exact Unconditional Test, we will perform a univariate logistic regression. NLMeans macro will be used to obtain the proportion difference and 95% confidence interval. There will be no adjustment for covariates

```
*** 1st dose comparison to Placebo (Sensitivity);
proc genmod data = d_1;
  title "1st dose comparison to Placebo (Sensitivity)";
  where group = 'HA/MCD' &
    ((dose = 'P1' & Placebo = 'Yes') |
    (dose = 'D1' & Placebo = 'No' ));
  class id dose;
  model resp(event = '1') = dose / dist=binomial link = logit;
  lsmeans dose / e ilink diff exp;
  store out=genmod;
  ods output coef = coeffs;
run;
%NLMeans(instore=genmod, coef=coeffs, link=logit, title= 1st dose
comparison to Placebo Prop Diff);
```

Handling of Missing Data

Participants with missing data for their placebo or 1st active dose will be removed from this analysis (complete case analysis).

Notes

The same analysis will be repeated for the Moderna COVID-19 Vaccine.

7.3.5. Secondary Endpoint 6

Endpoint: The proportion of participants who experience a systemic allergic reaction (CoFAR Grade 2 and above) within 48 hours of either dose of each vaccine.

Computation: A Grade 2 or higher systemic allergic reaction, categorized as yes or no, is defined as a participant having a Grade 2 or higher (per CoFAR Grading Scale V3.0) systemic allergic reaction within 48 hours to either active dose 1 or active dose 2 (categorized as yes) or to either active dose within 48 hours (categorized as no). Due to the nature of patient reported events, any systemic allergic reaction reported within 2 days after the date of injection will be counted as occurring within 48 hours.

Participants who do not have a systemic allergic reaction to the 1st active dose but missing data for their 2nd active dose will be removed from this analysis (complete case analysis).

Analysis: This analysis will be carried out as outlined in Section 7.2.2. A sensitivity analysis will be carried out as outlined in Section 7.2.3.

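### The programs in SAP 7.3.3–7.3.4 omit the version 1.0–4.0 restriction that SAP 7.3 sets, so as printed they admit children enrolled under versions 5.0–8.0

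*SAP*

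**What the plan says.** SAP 7.3 opens with the population: "All secondary endpoints will be analyzed for participants enrolled under version 1.0 through 4.0". It adds that, if enough children are enrolled, "then adults 18 years of age and older will be also be analyzed separately from children". Neither sentence provides for pooling version 5.0–8.0 children with the earlier participants.

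SAP 7.2.2 shows how the restriction is coded. The primary SAS program is subset by "where dose = 'E' and protocol<5", and its R counterpart and asymptotic fallback carry the same version condition. Secondary endpoints 1, 2 and 6 are analysed by reference to 7.2.2 and so inherit it.

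Sections 7.3.3 and 7.3.4 print seven further programs, none with a version condition:

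- Paired doses: the SAS McNemar program, limited only by "where group = 'HA/MCD"; the R equivalent; and the GEE model, limited by dose and group.
- Priming: the exact program and its logistic fallback, limited to HA/MCD and "dose = 'D1' & Placebo = 'Yes') | (dose = 'D2' & Placebo = 'No".
- First dose versus placebo: the exact program and its logistic fallback, limited to HA/MCD, with "dose = 'P1' & Placebo = 'Yes" for the placebo side and first doses of the vaccine-only arm for the other.

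Under versions 5.0–8.0 the protocol enrols only ages 5 to 17, randomised 2:1, initially to Pfizer or placebo + Pfizer (Protocol 3.5.1). A child given placebo first has the first vaccine dose at the "First Vaccination Visit (Day 8; + 14 Days" visit (Protocol 9.5.1). Protocol 3.5.2 says that participants, parents and "staff will be aware of whether a participant received placebo at the phone call 3 days after the first injection".

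**The concern.** A programmer who follows the listings would analyse a different population from the one SAP 7.3 states. The consequence differs by analysis.

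- **Priming.** The question is whether a second dose provokes more reactions than a first. Under versions 1.0–4.0 the two injections being compared fall at the same nominal visit, and both are given before placebo status is disclosed. The endpoint rests on graded symptoms, so both features matter. Children under versions 5.0–8.0 have neither.
- **First dose versus placebo.** The placebo arms of both vaccines are pooled, and the analysis is repeated for Moderna. Children randomised only between Pfizer and placebo + Pfizer would then be controls for a vaccine to which they could not have been assigned, and their share would differ between the two sides.
- **Paired.** Each participant is his or her own control, so the consequence that can be established is only that the population is not the stated one.

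**Working it through.** **1. Are the input data already restricted?** The priming and placebo programs read a long data set of the same name as the primary program. The primary program adds the version condition, which would be redundant if that data set held only versions 1.0–4.0. The paired SAS and R programs read a separate wide data set, on which the SAP says nothing either way.

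**2. What the children bring to each comparison.**

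| | Versions 1.0–4.0 | Versions 5.0–8.0 |
|---|---|---|
| Priming: first vaccine dose, placebo arm | Day 22 or 29 (Protocol 8.5.1) | Day 8 (9.5.1) |
| Priming: second dose, vaccine-only arm | Day 22 or 29 (8.4.1) | Day 22 or 29 (9.4.1) |
| Placebo status disclosed | Call 3 days after the second injection (3.1, 3.5.2) | Call 3 days after the first injection (3.5.2, 9.3) |
| Placebo comparison: both injections | Day 1, blinded (3.1) | Day 1, blinded (3.1) |

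For children the priming visits are nominally 22 − 8 = 14 days apart (Pfizer), or 29 − 8 = 21 days if the active vaccine is changed to Moderna.

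**3. Inputs.** Planned HA/MCD numbers (Protocol 14.7) are N = 1,020 per vaccine and C = 180 children. Allocation is 2:2:1:1, then 2:1 (Protocol 3.5.1), so it is 2:1 within a vaccine in both periods. The plan gives no child share to reproduce. The planned counts do return its zero-event upper limits: 1 − 0.025^(1/1020) = 0.0036 and 1 − 0.025^(1/180) = 0.020.

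Counts: 1,020 × 2/3 = 680 vaccine-only and 1,020 × 1/3 = 340 placebo-first per vaccine. For children, 180 × 2/3 = 120 and 180 × 1/3 = 60.

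**4. Share of children, vaccine restriction added.**

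- Pfizer priming, second dose: 120/(680 + 120) = 15.0%. First dose after placebo: 60/(340 + 60) = 15.0%. The 2:1 ratio cancels, so each share is C/(N + C). The pooled difference is about 0.85 × (version 1.0–4.0 difference) + 0.15 × (child difference).
- Placebo comparison, Pfizer first doses: 120/800 = 15.0%. Moderna first doses: 0/680 = 0%. Pooled placebo: 60/(340 + 340 + 60) = 60/740 = 8.1%.

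**5. Share with no vaccine filter, as literally printed.** Vaccine-only side: 120/(680 + 680 + 120) = 120/1,480 = 8.1%. Placebo-first side: 60/740 = 8.1%. This holds for priming and for the placebo comparison.

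**6. Sensitivity to enrolment.** These counts total 2,040 + 180 = 2,220 HA/MCD, above the 2,040 maximum in Protocol 3.1. Keeping to the maximum gives N = (2,040 − 180)/2 = 930, a priming share of 180/1,110 = 16.2% and a pooled placebo share of 60/(310 + 310 + 60) = 60/680 = 8.8%. Over N from 300 to 1,020 and C from 90 to 180, the priming share runs from 90/1,110 = 8.1% to 180/480 = 37.5%.

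**7. What the unequal shares in the placebo comparison could do.** Suppose there is no true effect, with a reaction rate of 1% in versions 1.0–4.0 and 5% in children. Both rates are assumptions for illustration.

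- Pfizer first doses: (680 × 0.01 + 120 × 0.05)/800 = 0.0160.
- Pooled placebo: (680 × 0.01 + 60 × 0.05)/740 = 0.0132.
- Spurious difference: +0.0028 for Pfizer; 0.0100 − 0.0132 = −0.0032 for Moderna.

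With 2% in children the differences are +0.0007 and −0.0008. With 0% they change sign.

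**The case against.** The governing text already gives the right population, and the listings look schematic. They have no vaccine filter, although each analysis is specified per vaccine, and the same is true of the primary programs. The primary R program joins its conditions with a word that is not an R operator. Subsetting may therefore happen outside the printed code, and a programmer who supplies the vaccine restriction from the text might supply the version restriction too. This stands as a limit on certainty: that children enter is what the code does as printed, not an established fact. It does not remove the mismatch, because version selection is visibly done inside the primary programs and missing only from those in 7.3.3–7.3.4.

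The harm to priming is also bounded. Allocation is 2:1 in both periods, so children are equally represented on the two sides. The result is a mixture of two contrasts, not an imbalance by age or period. That stands.

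A reader might infer that the placebo comparison also takes in unblinded children on a different schedule. The documents do not support this. Both of its injections are on Day 1, all versions are blinded to placebo versus vaccine at that visit, and the endpoint closes at 90 minutes, before the disclosure call.

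These analyses are secondary, and each has a zero-reaction condition under which it is not run. That limits the stakes but is no reason to leave the code inconsistent with the text.

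**Conclusion.** The printed programs for the paired, priming and first-dose-versus-placebo analyses contradict the population stated in SAP 7.3 and need correcting. It would be too strong to say that the secondary analyses as a whole are affected, since endpoints 1, 2 and 6 take the filter from 7.2.2.

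For priming, a blinded contrast at matched visits would be diluted with an unblinded one at unmatched visits. For the placebo comparison, the defect is unequal representation of children and the use of Pfizer-only children as Moderna controls.

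The size is conditional, because neither document gives enrolment by period. The 15%, 0% and 8% shares assume planned numbers, a vaccine restriction that the code lacks, and children enrolled only under Pfizer. Without the vaccine restriction the share is about 8% on each side. A switch of the child arm to Moderna would change the split. The spurious differences of up to about 0.003 rest on assumed rates and show direction and order of magnitude only.

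**What to change.** Add the version restriction to all seven programs in SAP 7.3.3–7.3.4: the paired SAS, R and GEE programs, the priming program and its fallback, and the placebo program and its fallback. In SAS this is the `protocol<5` condition already used in 7.2.2. In R the conditions should be joined with `&` or a comma, and the primary R listing should be corrected in the same way. The wide data set must carry the version variable.

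Alternatively, state in the SAP that the input data sets for these programs are limited to versions 1.0–4.0. It would help to say in the same place where the vaccine restriction is applied.

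Analyse version 5.0–8.0 children separately, and label their priming contrast as unblinded and not matched on visit.

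The cost is one condition per program and a sentence or two of text. With the filter, the planned Pfizer HA/MCD counts are 680 versus 340 for priming and 680 versus 680 for the placebo comparison. No new data are needed and no stated objective changes.

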#### 14.4.3. Analyses of Secondary and Other Endpoints

Similarly, the secondary analyses will estimate the proportion of participants with severe (Grade 3 or higher per [CoFAR Grading Scale for Systemic Adverse Reactions Version 3.0](#)) systemic allergic reactions within 90 minutes, Grade 2 or higher (per [CoFAR Grading Scale for Systemic Adverse Reactions Version 3.0](#)) within 48 hours, and anaphylactic reactions (Levels 1-3) per [Brighton Collaboration Criteria](#) within 90 minutes to either dose of the Pfizer-BioNTech COVID-19 Vaccine and independently to the Moderna COVID-19 Vaccine between the HA/MCD and comparison populations. Again, these estimates will be presented with their 95% exact confidence intervals. Due to the likelihood of these events to be extremely rare, no inferential analyses are planned.

An estimate of the proportion of participants with systemic allergic reactions to the first dose of the Pfizer-BioNTech COVID-19 Vaccine and independently the Moderna COVID-19 Vaccine in the HA/MCD population will be conducted. These estimates will be presented together with their 95% exact confidence intervals. Likewise, the estimate of the proportion and 95% exact confidence interval will be reported for the second dose conditional on no systemic allergic reaction to the first dose to each vaccine.

Another secondary analysis will be conducted to estimate the placebo-adjusted proportion of participants experiencing systemic allergic reactions to the first dose of either the Pfizer-BioNTech COVID-19 Vaccine and independently the Moderna COVID-19 Vaccine in the HA/MCD population. The placebo-adjusted proportions will be estimated as the differences in proportions between the first active vaccine dose versus the corresponding placebo vaccine arm. These estimates will be reported together with their corresponding 95% exact unconditional confidence intervals. Exact p-values will be calculated using an unconditional test. Details for implementation of the secondary analyses will be included in the statistical analysis plan.

Additionally, we will estimate the proportions of participants with systemic allergic reactions to the second vaccine dose (no placebo arm), first vaccine dose within the placebo arm, and their difference for the Pfizer-BioNTech COVID-19 Vaccine and independently the Moderna COVID-19 Vaccine in the HA/MCD population. These estimates will be presented together with their 95% exact confidence intervals.

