**Table 14.7. Expected Rates, Number of Systemic Allergic Reactions, and Sample Size**

Rate (Number) Sample Size	Pfizer-BioNTech COVID-19 Vaccine	Moderna COVID-19 Vaccine	Total (Sample)
Comparison (40%)	0.0001 (0) 680	0.0001 (0) 680	1360
HA/MCD (60%)	0.01 (10) 1020	0.01 (10) 1020	2040
Total	0.006 (10) 1700	0.006 (10) 1700	0.006 (20) 3400

Under the scenario described in [Table 14.7](#), the proportion difference within a vaccine between the two populations is estimated at 0.01 with an unconditional exact 95% confidence interval (0.003, 0.018) and unconditional exact test p-value < 0.05. This illustration shows the expected precision of the estimated proportion difference under the assumed scenario.

This sample size also allows the following precision for estimation of risk in the HA/MCD group within each vaccine sample. If no reactions are observed out of 1020, the corresponding exact 95% confidence interval is (0, 0.0036), which rules out a risk as high as 1/275. If instead, the observed proportion is 10/1020 (i.e., about 0.01), then the 95% confidence interval is (0.005, 0.018).

For children, the within vaccine sample size of 300 participants was chosen. Under this scenario, we expect 180 in the HA/MCD population and 120 in the comparison population. This will detect a minimum proportion difference between

the two populations of approximately 0.05 with approximately 80% power, assuming a two-sided unconditional exact test. The proportion is assumed to be 0.0001 (1/10,000) in the comparison group and 0.05 (1/20) in the HA/MCD group.

Furthermore, a sample size goal of 300 children into the Pfizer-BioNTech COVID-19 vaccine allows for the following precision for the estimation of risk in the HA/MCD group. If no reactions are observed out of the 180 HA/MCD participants, the corresponding exact 95% confidence interval is (0, 0.020), which rules out a risk as high as 1/50. If instead the observed proportion is 2/180 (i.e., about 0.01), then the 95% confidence interval is (0.001, 0.039).

The sample size calculations do not account for dropouts since we expect that number to be extremely low. Although vaccine is widely available, there are difficulties getting into the registration systems and few individuals who receive an initial dose do not return for the second dose.

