    ((dose = 'D1' & Placebo = 'Yes') | (dose = 'D2' & Placebo = 'No'));
  class dose;
  model resp(event = '1') = dose / dist=binomial link = logit;
  lsmeans dose / e ilink diff exp;
  store out=genmod;
  ods output coef = coeffs;
run;
%NLMeans(instore=genmod, coef=coeffs, link=logit, title= Priming Prop
Diff);
```

Handling of Missing Data

Participants with missing data for their 2nd active dose for reasons other than systemic allergic reactions in their 1st active dose will be removed from this analysis (complete case analysis).

Participants with missing data for their 2nd active dose because of a systemic allergic reaction to their 1st active dose (inherent missingness given the current design) will be examined using an extreme case scenario (replacement of all 2nd active dose missing by either yes or no). If the result from this extreme case scenario differs and if there is at least 10 systemic allergic reactions in the 1st active dose a tipping point analysis will be conducted.

Notes

The same analysis will be repeated for the Moderna COVID-19 Vaccine.

7.3.4. Secondary Endpoint 5

Objective (First dose comparison to Placebo)

Assess the proportion of participants with systemic allergic reactions to the Pfizer-BioNTech COVID-19 Vaccine in the HA/MCD after adjusting for placebo

Endpoint

The proportion of participants who experience a systemic allergic reaction (CoFAR Grade 2 and above regardless of tryptase, or CoFAR Grade 1 with elevated tryptase [1.2 x baseline plus 2 ng/ml]) within the 90-minute post-vaccination observation period to the first dose of the Pfizer-BioNTech COVID-19 Vaccine after adjusting for placebo administration

Model Specification

- Endpoint is as defined above.
- Endpoint will be analyzed using Barnard's unconditional exact test.

Model Checking & Diagnostics

This analysis will not be carried out if there are no systemic allergic reactions for the placebo dose.

Model Results Presentation

Proportion difference, 95% exact unconditional confidence interval and p-value will be presented for the comparison between 1st dose (active arm) and placebo dose (placebo arm)

Placebo + Pfizer-BioNTech/Placebo + Moderna COVID-19 Vaccine (**placebo**) vs Pfizer-BioNTech COVID-19 Vaccine (**1st**)

Placebo + Pfizer/Placebo + Moderna	placebo	1st	2 nd
Pfizer	1 st	2 nd	

SAS Code

```
*** 1st dose comparison to Placebo;
proc freq data = d_1;
  title "1st dose comparison to Placebo";
  where group = 'HA/MCD' &

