11. CHANGES TO THE ANALYSES PLANNED IN THE PROTOCOL

As treated sample definition was updated to reflect placebo analyses.

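### SAP 7.3.4 drops the first-dose-versus-placebo analysis when no placebo reaction occurs, a condition absent from Protocol 14.4.3 and not listed in SAP Section 11

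*SAP*

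**What the plan says.** Protocol 14.4.3 defines the estimate: "The placebo-adjusted proportions will be estimated as the differences in proportions between the first active vaccine dose versus the corresponding placebo vaccine arm". It adds exact unconditional 95% intervals and exact unconditional p-values, separately for each vaccine, in HA/MCD participants. No minimum number of events is required. Implementation details are left to the SAP.

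SAP 7.3.4 uses Barnard's test and then sets a condition under Model Checking & Diagnostics: "This analysis will not be carried out if there are no systemic allergic reactions for the placebo dose". Three other parts of the SAP bear on this:

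- **Comparator (7.3.4).** The placebo side is given as "Placebo + Pfizer-BioNTech/Placebo + Moderna COVID-19 Vaccine", so both placebo arms are combined.
- **Fallback (7.3.4).** "If there is an issue with the calculation of the Barnard's Exact Unconditional Test, we will perform a univariate logistic regression", with the NLMeans macro converting the result to a difference.
- **Priming analysis (7.3.3).** A similar condition cancels that analysis if there are no "systemic allergic reactions in the 1st dose among the placebo arm and/or 2nd dose among the Pfizer arm".

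SAP Section 11 has a single entry: "As treated sample definition was updated to reflect placebo analyses".

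**The concern.** Whether a planned estimate is reported should not depend on the count in its own control group. Placebo here is saline, so zero placebo reactions is a natural outcome. It is also the result that most clearly attributes first-dose reactions to the vaccine, and it is the one case in which the SAP drops the contrast.

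The endpoint matters because it is the only planned randomised vaccine-versus-placebo comparison of the systemic-allergic-reaction endpoint. The primary comparison, HA/MCD against the comparison population, is not randomised. The Fisher tests in SAP 8.2 compare adverse event types by arm and do not use the 90-minute CoFAR/tryptase definition.

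There is also a selection effect. When the analysis does run, the placebo rate has been selected to be above zero, so the difference is biased downward.

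**Working it through.** **1. Does a zero cell stop the calculation?** In the plan's own example (Protocol 14.7, Table 14.7: about 10 of 1020 against 0 of 680), "the proportion difference within a vaccine between the two populations is estimated at 0.01 with an unconditional exact 95% confidence interval (0.003, 0.018"), with p below 0.05. Recomputing 10/1020 against 0/680 with Barnard's test (score ordering, one-sided p maximised over the nuisance rate and then doubled, the convention of SAP 7.2.2) gives p = 0.012. The score-based upper limit is 0.018, as stated. The lower limit came out at 0.0022 with the full nuisance range and 0.0038 with the nuisance rate limited to 0.02, so the stated 0.003 is bracketed but not matched exactly. The method plainly works with a zero cell.

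**2. Group sizes.** There are 2040 HA/MCD participants (Protocol 3.1), randomised 2:2:1:1. Active-first is 2040 × 2/6 = 680 per vaccine. Placebo-first is 2040 × 1/6 = 340 per vaccine, or 680 pooled. These are upper bounds, because SAP 7.3 says "All secondary endpoints will be analyzed for participants enrolled under version 1.0 through 4.0".

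**3. Chance of cancellation and the selection effect.** For a true placebo rate p and n placebo recipients, P(cancelled) = (1 − p)^n. The mean observed placebo rate given that the analysis runs is p / [1 − (1 − p)^n]. For example, at p = 0.001 and n = 680, 0.999^680 = 0.506 and 0.001/0.494 = 0.00203. No placebo rate is documented, so a range is assumed.

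| Assumed rate | Cancelled, n = 680 | Cancelled, n = 340 | Mean rate if run, n = 680 | Mean rate if run, n = 340 |
|---|---|---|---|---|
| 0.01% | 93% | 97% | – | – |
| 0.1% | 51% | 71% | 0.203% | 0.347% |
| 0.2% | 26% | 51% | 0.269% | 0.405% |
| 0.5% | 3% | 18% | 0.517% | 0.611% |
| 1% | 0.1% | 3% | 1.001% | 1.034% |

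**4. What is suppressed.** Doubled one-sided Barnard p-values for 680 vaccine first doses:

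| Reactions, vaccine v placebo | 680 pooled placebo | 340 own-arm placebo |
|---|---|---|
| 5 v 0 | 0.026 | 0.14 |
| 6 v 0 | 0.014 | 0.14 |
| 7 v 0 | 0.0085 | 0.084 |
| 10 v 0 | 0.0015 | 0.032 |
| 6 v 1 | 0.070 | – |

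For scale, the 1% planning rate covers either dose, so it implies at most about 0.01 × 680 = 6.8, or 7, first-dose reactions.

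**5. What would be reported without the condition.** For 7/680 against 0/680 the difference is 0.0103, with a score-based exact 95% interval of about (0.0035, 0.021). Against 0/340 the difference is the same and the interval is about (−0.002, 0.021).

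**6. The fallback.** With a zero cell, the maximum-likelihood log odds for that group is infinite, so the logistic model and NLMeans have no finite estimate.

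**The case against.** The strongest defence is that Protocol 14.4.3 leaves implementation to the SAP and that little is lost. With zero placebo reactions, the point difference equals the first-dose proportion in the active-first arm. First-dose rates are still reported in SAP 7.2.4, and in 7.3.3 with exact intervals. This narrows the loss to the planned difference, its interval and one p-value for a secondary endpoint. It does not remove it: an interval for a single proportion carries none of the uncertainty about the placebo rate (exact 95% upper limit 0.54% for 0/680, 1.08% for 0/340). Deciding from the data whether a planned estimate appears at all goes beyond implementation.

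Four further points have some force:

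- **The 6 v 0 example needs the pooled comparator.** Against the protocol's own arm of 340, no count up to 7 v 0 is significant, so at or below the planning rate no significant test would be hidden. The loss of the estimate and interval remains.
- **The bias is small.** With pooled placebo it is about 0.10 percentage points at a true rate of 0.1% and 0.07 points at 0.2%, against an interval about 1.75 points wide in the 7 v 0 example.
- **Pooling is defensible.** Both placebos are saline and randomisation was concurrent. It still departs from the protocol's wording and is not listed in Section 11.
- **The fallback problem is mostly dormant today.** The condition stops the analysis before a zero placebo cell can reach the logistic model. It becomes live once the condition is removed, so the two need changing together.

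**Conclusion.** The concern holds. SAP 7.3.4 adds a data-dependent cancellation that Protocol 14.4.3 does not contain, that the method does not need, and that Section 11 does not record. How likely it is to take effect depends on an undocumented placebo rate: with pooled placebo the probability runs from 93% at 0.01% to 0.1% at 1%. Those figures assume full accrual; with fewer placebo recipients, cancellation is more likely at any given rate. Whether a significant result would be hidden depends on the comparator, which the two documents describe differently (7 v 0 gives 0.0085 pooled and 0.084 against the own arm). The downward bias matters only if the true placebo rate is about 0.2% or less with pooled placebo, and even then it is modest.

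The priming condition in 7.3.3 has a related defect: its conjunction can be read as cancelling the analysis when only one of the two groups has no reactions. Protocol 14.4.3 plans those proportions and their difference without a condition.

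**What to change.** 1. Delete the condition in SAP 7.3.4. Always report the first-dose minus placebo difference with its exact unconditional interval, and run Barnard's test unless both groups have zero reactions.
2. Do not use the logistic/NLMeans fallback when any cell is zero. Name an exact alternative for that case.
3. In the priming analysis (7.3.3), reword the condition so that the test is skipped only when both groups have zero reactions, keep the proportions, difference and intervals in every case, and apply the same fallback rule.
4. Choose the pooled or the vaccine-specific placebo arm as the main comparator, and give the other as a sensitivity analysis.
5. List these changes in SAP Section 11.

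The cost is a few sentences of SAP text. The main PROC FREQ call handles one zero cell unchanged; only the logistic fallback needs replacing for that case.
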